13.1.16 MTX Delays and Dose Modifications

MTX is a weekly medication; side-effects tend to be most noticeable in the 24-28 hours after taking each dose. For this reason, participants may wish to delay their first MTX dose for up to two weeks after the baseline visit. Scheduled dates and windows of blood monitoring tests should be scheduled in accordance with the date MTX is commenced rather than with the baseline visit.

Participants may immediately reduce their MTX dose in the event of toxicity or side-effects but should contact their rheumatologist as soon as possible to discuss other appropriate management.

Please also see section 13.4.1 regarding Laboratory Abnormalities and Infections.

13.1.17 Antibiotic Use

In the event of an acute infection requiring antibiotic therapy, MTX should be omitted until after the course of antibiotics has ended and the participant has recovered from their infection. Participants should contact the site as to when they should resume taking MTX; they may be advised to re-start it initially at a lower dose and then re-escalate to maximum tolerated dose. The reason for starting at a lower dose is that the gut microbiome is involved in methotrexate metabolism and may be disturbed by some broad-spectrum antibiotics.

13.1.18 Renal Impairment

Methotrexate is excreted via the kidneys and MTX dosing should be reviewed in the event of acute renal impairment.

13.1.19 Most frequently anticipated toxicities of MTX

In a systematic literature review (47), the pooled prevalence of adverse effects was 80.1% in RCTs of MTX, and 23% in observational studies. In RCTs 6.7% discontinued MTX due to adverse effects, whereas in observational studies 15.5% discontinued due to adverse effects.

Commonly reported side-effects of methotrexate include nausea (19.2% in RCTs), altered taste, abdominal pain or discomfort (9.3% in RCTs), diarrhoea (8.0% in RCTs), headache (8.5% in RCTs), dizziness (7.2% in RCTs), fatigue, and thinning of the hair (6.9% in RCTs) and mouth ulcer or soreness (7.8% in RCTs). These are often easily noticed by the participant because of the weekly administration. In this trial, these well-known adverse effects of MTX are not necessarily considered “toxicities” unless they are troublesome to the participant. Folic acid, 5mg up to six days per week, may help to alleviate many of these common side-effects. Management advice may also include review of diet, smoking cessation, mouthwashes for sore mouth or simple analgesia for headache, at the clinician’s discretion. An extra cup of strong coffee, or dark chocolate, the morning after MTX administration is sometimes recommended on the basis that caffeine antagonises adenosine signalling in the central nervous system and might alleviate the central nervous system side-effects of MTX (48).

MTX may cause mild cytopenia including neutropenia. Neutrophil counts below $1 \times 10^9/L$, if persistent on rechecking, would be an indication to stop MTX. Pancytopenia is rare and usually only seen in MTX overdose.

MTX-related pneumonitis is an idiosyncratic reaction and is very rare (47): it was reported in <0.1% of participants in RCTs.

Abnormalities of liver function tests including AST/ALT are frequently observed in patients receiving MTX; in the meta-analysis (47) the pooled prevalence of any elevated liver enzyme was 15.3% in 6 RCTs. The concern is that MTX may have a profibrotic effect; it is contra-indicated in participants who already have liver cirrhosis. A study of liver stiffness using Fibroscan (49) in participants receiving MTX showed no correlation with cumulative MTX exposure but significant correlations with markers of obesity (body mass index, waist circumference).

Blood monitoring tests during MTX treatment commonly show a minor rise in the mean cell volume (mcv). This is benign and is due to the polyglutamation of MTX inside erythrocytes. In rheumatoid arthritis, a rise in mcv during MTX treatment has been reported to be associated with better therapeutic response to MTX.

13.1.20 Methotrexate and pregnancy

MTX must not be taken in pregnancy as it is a teratogen. In line with the SmPC MTX must be stopped six months in advance of trying to conceive in both male and female participants and contraception (see appendix 2) must be used for this period. In the case of male participants, the contraceptive measures can be taken by either themselves or their female partners. In the event of unplanned pregnancy MTX must be stopped immediately.

13.2 SWITCHING TO LEFLUNOMIDE

The beneficial effects of MTX in rheumatic diseases are generally quoted as taking at least 3 months to accrue. If MTX is not tolerated therapy may be switched to the second line DMARD, LEF.

13.2.1 Site Research Team Activities Upon Transfer to LEF

- Update the participant's record on the STERLING Participant ID Log by adding details of the treatment allocation.
- Notify the participant's GP of their transfer to LEF.
- Discuss with the participant the situations in which it would be most appropriate to seek support from the site research team and the situations where it is more appropriate to approach their GP for advice.
- Provide the participant with a Blood Pressure monitoring device and explain to participants how and when (see section 13.3.4) this should be used.
- Prescribe an initial 6-week supply of leflunomide following local procedures. It is the prescriber's responsibility to ensure that participants are counselled about the importance of how and when to take their leflunomide. To ensure that participants receive up to date counselling and the same safety procedures as participants in routine care, participants will be provided with written participant information materials that would be provided for participants starting a DMARD in routine care, for example booklets produced by the independent charity Versus Arthritis, to supplement the verbal information given.
- Issue paper or electronic DMARD monitoring blood tests laboratory request forms for the duration of the initial leflunomide prescription, with clear instructions for the participant about the time windows during which each test must be done, and the options they have for the blood draw (e.g., by appointment with their GP practice, or by visiting the site by appointment or at a local pathology clinic.). The participant will need to arrange their own blood tests, except where this falls within the clinic visit schedule.

- Specifically remind the participant that if they develop an intercurrent infection they may need to stop their DMARD (but continue steroid) and inform the hospital team for advice on when the DMARD can be re-started.

13.3 LEFLUNOMIDE REGIMEN

13.3.1 MTX wash-out

MTX must be stopped before LEF is commenced (they should not be taken together in this trial).

MTX polyglutamates may be retained in tissues for some weeks after MTX cessation, and therefore a wash-out period of at least 2 weeks is recommended before starting LEF; this may be extended to 8 weeks where required.

13.3.2 LEFLUNOMIDE CONTRAINDICATIONS

Leflunomide must not be commenced if contra-indicated in the opinion of the local Investigator. This includes:

- hypersensitivity to leflunomide
- uncontrolled hypertension*
- current active infection** at the time of commencement. In this case, leflunomide treatment may be deferred and started after the infection has resolved.

* BP higher than 145/95 measured at study visit and over 140/90 when measured at home or in the community within 6 weeks prior to the proposed commencement of leflunomide

- ** including but not restricted to AIDS, active tuberculosis infection or other serious infection

13.3.3 Leflunomide Pre-treatment Investigations

The following investigations are required before commencing leflunomide:

- Blood pressure
- Full blood count (FBC), including differential white cell count and platelet count
- Liver function tests (LFT) including alanine aminotransferase (ALT) and albumin
- Urea and electrolytes (U+E) including estimated glomerular filtration rate (eGFR)
- Pregnancy test where participant is a woman of child-bearing potential

A chest radiograph will have been performed prior to commencing MTX therapy and therefore does not require repeating prior to commencing LEF.

Providing the above blood tests have been performed within the preceding 6 weeks and the results do not fall outside the limits referred to in section 13.4.1 and are acceptable according to local physician discretion there is no need to repeat these prior to commencing LEF.

Where the latest results are either outside acceptable parameters or have been done more than 6 weeks ago these will need repeating and found to be within acceptable parameters before commencing LEF.

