4. A medical condition other than PMR that has required >2 courses of systemic glucocorticoid treatment lasting 5 days or more, or any course lasting 30 days or more, during the year prior to randomization.
5. Giant cell arteritis (previous or current) in the opinion of the local investigator.
6. Rheumatoid arthritis, psoriatic arthritis or spondyloarthritis (previous or current) in the opinion of the local investigator
7. At the baseline visit active infection of sufficient severity to be a contra-indication to commencing methotrexate, in the opinion of the local investigator.
8. Participant taking concurrent trimethoprim-sulfamethoxazole at the time of the baseline assessments
9. Active gastric ulcer at the baseline visit in the opinion of the local investigator
10. Known prior history of a significant immunodeficiency syndrome, defined as an immunodeficiency severe enough to cause recurrent infections of frequency or severity that in the opinion of the investigator would preclude DMARD treatment
11. Known prior history of hereditary galactose intolerance, hereditary total lactase deficiency or hereditary disorder of glucose-galactose malabsorption
12. Current treatment with folate antagonists including trimethoprim-sulfamethoxazole
13. Other medical condition that in the opinion of the local investigator is severe enough to seriously compromise evaluation of the primary or key secondary endpoints
14. Treatment with any immunosuppressive therapy (conventional synthetic, targeted synthetic or biological DMARD) within 3 months prior to randomisation.
15. Treatment with any investigational drug in the last 4 months prior to the start of protocol treatment.
16. Unable to complete essential study procedures and communicate with study staff independently.
17. Participants must NOT fulfil any of the following within 6 weeks prior to baseline: Haemoglobin <10.0 g/dL; total white cell count <3.5 x10⁹/L; absolute neutrophil count <1.5 x10⁹/L; platelet count <100 x10⁹; ALT (alanine aminotransferase) or AST > 2 x upper limit of reference range for the laboratory conducting the test, eGFR (estimated glomerular filtration rate) <30ml/min

18. Evidence of respiratory disease on chest radiograph (performed during screening or within the 6 months prior to screening) of sufficient severity to be a contra-indication to commencing methotrexate, in the opinion of the local investigator.

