13.4 PROCESSES AND CONSIDERATIONS COMMON TO BOTH DMARDS

13.4.1 Laboratory Abnormalities and Infections

A temporary DMARD treatment interruption may be required (managed at the investigator's discretion) under circumstances such as those described below.

Abnormal LFTs

- ALT or AST elevation of ≥ 3 times ULN, dose interruption is recommended.
- ALT or AST elevation $\geq 5x$ ULN, discontinuation of DMARD treatment is recommended.
- If ALT or AST elevation of ≥ 3 times ULN and
 - Total bilirubin $> 2x$ ULN or INR > 1.5 ULN, and
 - Alkaline phosphatase $> 2x$ ULN and
 - Presence of worsening fatigue, nausea, vomiting, fever, rash, or eosinophilia,discontinuation of treatment is recommended.

Infections

Clinical signs which suggest the possibility of drug toxicity may include severe or frequent minor infections, mucositis and pneumonitis and should be interpreted by the investigator and lead to dose interruption if indicated. Multiple dosing interruptions up to 8 weeks at any one time are allowed if necessary.

Neutropenia

Absolute neutrophil count decrease should be managed according to clinical judgment; a decrease to $< 1 \times 10^9/L$ ($1 \times 10^3 /\mu L$) should however result in treatment interruption. Study treatment should commence after increase of the neutrophil count to $\geq 1 \times 10^9/L$ and in line with clinical judgment. Treatment is continued as long as no further safety concerns arise. Multiple dosing interruptions up to 6 weeks at any one time are allowed if necessary.

The participant's welfare is the responsibility of the investigator. Therefore, the investigator must decide, based on risk-benefit assessment, what is needed to ensure the safety of the treatment. These options include deciding when unscheduled or repeat laboratory testing is indicated, and if a temporary interruption or discontinuation of treatment +/- concomitant medication is appropriate.

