14.4 SCREENING ASSESSMENTS

Trial screening assessments should take place after written informed consent has been obtained and after registration on the CTRU 24-hour Registration system has been completed. Trial Screening assessments are designed to establish participant eligibility to enter the trial and include the following assessments listed below.

- Physical examination - cardiorespiratory, abdominal, skin, head/eyes/ENT, and screening neurological exam, as well as MSK system including elevation of upper limbs, joint swelling/tenderness/limitation of movement, and vascular including temporal arteries
- Chest X-Ray: a report from a chest x-ray performed within last 6 months prior to the screening visit is acceptable to confirm eligibility providing that no evidence of interstitial lung disease or tuberculosis or active infection.
- Pregnancy test for women of childbearing potential
- Rheumatoid factor (RF) test – result from any test performed within last 12 months prior to the screening visit is acceptable to confirm eligibility.
- Anti-citrullinated peptide antibody (ACPA) test – result from any test performed within last 12 months prior to the screening visit is acceptable to confirm eligibility.
- Urea & Electrolytes (U&E) test
- Full blood count
- Liver function test
- CRP
- Vital Signs – including, BP, heart rate, temperature

Where local guidelines apply stricter suitability criteria than those listed below then the local criteria should be applied. However, the following should be applied as a minimum/maximum acceptable parameter:

- Haemoglobin <10.0 g/dL
- Total white cell count <3.5 x10⁹/L
- Absolute neutrophil count <1.5 x10⁹/L
- Platelet count <100 x10⁹/L
- ALT (alanine aminotransferase) or AST > 2 x upper limit of reference range for the laboratory conducting the test
- eGFR (estimated glomerular filtration rate) <30ml/min

Confirmation that the participant meets all other eligibility criteria can be obtained via a combination of i) review of their medical notes or information provided by their GP as part of the referral process and ii) taking the medical history of the participant at the screening visit.

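### The leflunomide start check in 13.3.3 borrows its only numeric blood limits from the on-treatment interruption levels in 13.4.1, which leaves a weak numeric floor for first exposure to a second DMARD

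*Protocol*

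**What the plan says.** Protocol 13.3.3 lists the investigations needed before LEF: blood pressure, full blood count with differential and platelets, liver tests, urea and electrolytes with eGFR, and a pregnancy test where relevant. Blood results from the preceding 6 weeks need no repeat if "the results do not fall outside the limits referred to in section 13.4.1 and are acceptable according to local physician discretion". If the latest results are older than that or not acceptable, "these will need repeating and found to be within acceptable parameters before commencing LEF". No values accompany that second condition.

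Section 13.4.1 applies to both DMARDs and opens by saying "A temporary DMARD treatment interruption may be required". Its liver rule is "ALT or AST elevation of ≥ 3 times ULN, dose interruption is recommended", with discontinuation at 5 x ULN or more. Its neutrophil rule is interruption below 1 x 10⁹/L. After that, "Study treatment should commence after increase of the neutrophil count to" at least 1 x 10⁹/L.

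Exclusion 17 in 8.2 sets six blood limits for randomisation, among them "ALT (alanine aminotransferase) or AST > 2 x upper limit of reference range for the laboratory conducting the test". Section 14.4 repeats the six, stating that "the following should be applied as a minimum/maximum acceptable parameter", and lets stricter local criteria prevail. Section 13.1.1 describes the screening assessments as a check of fitness for methotrexate (MTX).

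Section 13.3.2 adds a general safeguard: "Leflunomide must not be commenced if contra-indicated in the opinion of the local Investigator". Its list of contraindications is open, and its only numeric limits are for blood pressure.

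**The concern.** A level at which treatment under way should be interrupted is not necessarily a suitable level at which to begin a new drug. Section 13.3.3 orders a full blood count and names the platelet count, then points to a section with no platelet, haemoglobin or total white cell value. For liver enzymes it points to a level higher than the one that would have kept the same person out of the trial.

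LEF is also the written default after MTX: 13.1.14 says participants go on to it once MTX is stopped, unless contraindicated (13.2 is more permissive). Some will have stopped MTX because of toxicity. Section 13.1.19 cites any elevated liver enzyme in 15.3% of MTX recipients across 6 RCTs and says mild cytopenia can occur. Section 13.3.13 lists raised liver tests and cytopenia among LEF toxicities and warns that they can outlast treatment because of the long half-life. What is at stake is participant safety and consistency between sites.

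**Working it through.** No sample size, power or error rate is involved. The check sets the numeric limits side by side.

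| Test | Before randomisation / MTX (8.2 exclusion 17; 14.4) | Limit that 13.3.3 takes from 13.4.1 | Result |
|---|---|---|---|
| ALT or AST | >2 x ULN bars entry | ≥3 x ULN | Above 2 and below 3 x ULN passes |
| Haemoglobin | <10.0 g/dL bars entry | none | No numeric floor |
| White cells | <3.5 x 10⁹/L bars entry | none | No numeric floor |
| Platelets | <100 x 10⁹/L bars entry | none | No numeric floor |
| Neutrophils | <1.5 x 10⁹/L bars entry | <1.0 x 10⁹/L | 1.0 to below 1.5 passes; 1.0 is a stated resumption level |
| eGFR | <30 ml/min bars entry | none | Absent; the protocol's renal caution concerns MTX |

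1. Liver enzymes: the gap is 3 − 2 = 1 x ULN. The compound liver rule in 13.4.1 also starts at 3 x ULN, so it does not close the gap.

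2. Haemoglobin, white cells and platelets: 13.3.3 requires the full blood count, but 13.4.1 supplies none of these three values. Section 13.3.2 supplies none either.

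3. Neutrophils: the difference is 1.5 − 1.0 = 0.5 x 10⁹/L. Because 13.4.1 expressly accepts treatment at 1.0 x 10⁹/L or above, this may be deliberate and is not counted as a gap.

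4. eGFR: it is a required test with no value in 13.4.1. Sections 7.5.2, 13.1.9 and 13.1.18 tie renal caution to MTX, so this is a question for the clinical team and is not counted either.

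5. Tally of the six limits: 1 looser (ALT/AST) + 3 absent (haemoglobin, white cells, platelets) + 2 left open (neutrophils, eGFR) = 6.

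6. Illustration: an ALT of 2.5 x ULN, or platelets of 80 x 10⁹/L, would each have barred entry. Each passes every numeric limit that 13.3.3 invokes for LEF, and only the physician's judgement remains. Likewise, someone taken off MTX at 5 x ULN or more would pass numerically once below 3 x ULN.

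**The case against.** There is a good case on the other side, and most of it stands as a limit on the point.

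- Read literally, the sentence citing 13.4.1 waives repeat testing; it is not a stand-alone start rule. That is right. For recent results, however, the waiver works as the numeric gate, and the paragraph on repeat tests gives no values of its own.
- The stricter values are randomisation and MTX-fitness limits. Nothing says that they govern LEF. A reader might infer that the protocol contradicts itself or breaches its own exclusion; it does neither. Those values are a comparator only.
- Section 13.4.1 is the in-trial standard elsewhere too: 12.6 uses it before each new MTX prescription and 13.1.11 before MTX escalation. That makes the cross-reference coherent. But both uses concern a drug the participant is already taking, whereas LEF is a first exposure.
- Discretion is preserved in 13.3.2, 13.3.3 and 13.4.1, and guide monitoring after starting LEF is every two weeks at first (13.3.4). A reader might infer that unsafe starts follow automatically; the text does not support that. Still, 14.4 also leaves room for local judgement and sets a numeric floor beneath it, so the protocol did not rely on judgement alone for the first DMARD.
- The documents do not establish 2 x ULN as the right LEF threshold. That stands, and is why the change should remain subject to clinical confirmation and discretion.

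**Conclusion.** The point holds as a modest one, for the sponsor to consider. The numeric floor for starting LEF is weak: it is looser than the protocol's only pre-DMARD limit for ALT/AST, and missing for three blood count values whose tests 13.3.3 requires. The similar wording on acceptable parameters in 14.4 suggests, without proving, that limits of that kind were intended.

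The number of participants affected is unknown and probably small. The protocol gives no distribution of results at the time of switching, so no estimate is offered. The primary analysis is unaffected. The conclusion assumes that 'acceptable parameters' in 13.3.3 refers back to 13.4.1, the only limits that the section cites. If it means something else, the term is undefined and the same fix applies.

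**What to change.** In 13.3.3, define 'acceptable parameters' for starting LEF by the 14.4 values: ALT and AST not above 2 x ULN, haemoglobin not below 10.0 g/dL, white cells not below 3.5 x 10⁹/L and platelets not below 100 x 10⁹/L, all subject to physician discretion. Apply the definition both to recent results and to repeat tests. Ask the clinical team to confirm the neutrophil level (1.0 or 1.5 x 10⁹/L) and whether the eGFR limit should apply. Keep 13.4.1 for interruption and resumption of treatment under way.

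The change is to protocol wording only, since 13.3.3 already requires every test. The downside is that a few LEF starts would be delayed or refused, mainly in participants with residual ALT of 2 to 3 x ULN after MTX. Some of that delay may fall within the MTX wash-out of 2 to 8 weeks in 13.3.1; how much cannot be judged from the protocol.

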13.3.4 Ongoing Blood monitoring and Blood therapy

Pressure Assessments during Leflunomide

Monitoring of leflunomide via blood tests and blood pressure measurements will follow local recommendations. As a guide the British Society for Rheumatology DMARD monitoring guidelines recommend FBC, U+E, LFT and a blood pressure measurement:

- every two weeks until on stable dose for six weeks
- monthly for three months and
- quarterly thereafter

Blood Tests

The site team will issue sufficient laboratory request forms to cover the duration of each prescription and will check the results of the monitoring blood tests before each new prescription of LEF is issued.

Providing the results of the prior tests do not fall within the limits referred to in section 13.4.1 and are acceptable according to local physician discretion, windows either side of these blood monitoring dates will be allowed. Please see Schedule of Events for details of appropriate windows.

Blood Pressure

Blood pressure (BP) should be measured at the same time as each blood test. Participants who transfer onto LEF from MTX will be issued with their own blood pressure monitor. Therefore, it is acceptable for the BP to be measured either by the GP practice or self-managed by the participant. Participants will receive instruction from the research team regarding the use of the monitor and written instructions advising them that:

- should the BP value be over 140/90 then it should be rechecked on another occasion within one week. If on re-checking, it is still over 140/90, then the site research team should be notified within one further week.
- should the BP value be over 180/120 (regarded as severe hypertension), the research team should be contacted on the next working day so that appropriate clinical action can be taken.

The team will promptly communicate new or significant findings of high blood pressure to the GP, as this may require escalation of antihypertensive therapy by the GP.

